2. Self-report smoking at least 5 cigarettes per day for the past year
3. Breathe carbon monoxide (CO) level > 8 ppm or positive urine NicCheck
4. Willingness to use other tobacco products during the study
5. Speak, comprehend, and read English sufficiently to complete study procedures
6. Have home access to a computer, smart phone, or tablet with a web camera and internet access
7. Tried a vaping device at least once in their lifetime

Exclusion criteria:

1. Currently seeking treatment to quit smoking
2. Self-reported serious medical or psychiatric condition(s) including cardiovascular and chronic respiratory diseases
3. Body temperature > 100.4 F

4. Cold, flu or COVID-19 symptoms including fever, cough, and runny nose in the past 30 days
5. Currently pregnant, breastfeeding or intending to become pregnant for the duration of the study or unwilling to agree to use adequate protection to avoid pregnancy
6. CO reading > 80 ppm

Those with unstable medical or psychiatric conditions are excluded as these symptoms could affect a participant's ability to complete the study and how they make decisions about what tobacco products to use. We will exclude those indicating immediate readiness to stop smoking, as participation in this study may not lead to reductions in smoking. We will exclude pregnant people, those trying to become pregnant and those currently breastfeeding due to the potential harmful effects of tobacco use on developing fetuses and infants. Because participants are required to complete portions of the protocol independently during the virtual lab sessions, they will need to be able to independently read and comprehend the study materials.

Those who report past 30 day cold, flu or COVID-19 symptoms will be temporarily excluded as a safety precaution. They will be able to re-screen once they have been symptom-free for more than 30 days.

Telephone Screening Survey

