In-Person Lab Visit 2 will be completed up to 48 hours after completing Virtual Visit 5. Participants will complete the COVID screener within 24 hours of their Lab visit via email or phone. Research staff will wear personal protective equipment during the visit including face masks and gloves. The participants will be required to wear facemasks when interacting with the staff. Temperature checks will be conducted immediately upon arrival using a thermal heat scanner.

Participants will provide CO readings be at least 6-feet away from other people, including the research staff, while they have their masks off.

Participants will be given the products they purchased during the ETM task and will be instructed to only use these products for the next seven days. They will also be given a urine collection cup and instructions for sample collection.

The field assessment validates the ETM task by having participants use the products in the real world, simulating the different regulatory environments. Actual product use enables us to measure their subjective experiences such as withdrawal, craving, or product satisfaction as well as assess changes in carbon monoxide exposure, a biomarker of harm, when using products other than menthol cigarettes. We will conduct between-subjects analyses comparing these secondary outcomes by marketplace condition.

Virtual Visit 6

Participants will complete Virtual Session 6 seven days after completing In-Person Lab Visit 2.

The following baseline assessments will be administered as an interview and entered into REDCap by the interviewer:

1. Timeline Follow Back (TLFB) Questionnaire which will assess past tobacco and nicotine product use since Virtual Visit 5.

The following surveys will be self-administered using REDCap:

1. Tobacco Policy Questionnaire
2. Minnesota Nicotine Withdrawal Scale
3. Questionnaire of Smoking Urges-Brief – Usual Brand Cigarette
4. Product Evaluation Scale – VLNC, E-Cigarette, Gum (whichever product(s) they select)
5. Perceived Health Risks Scale
6. Tobacco Product Interest Scale
7. Health Changes Questionnaire

Participants will complete the ETM task under the same marketplace condition from which they received their field assessment products. Exploratory pre-post field assessment analyses will examine how actual use of the products affects subsequent purchasing of those products.

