While participating in the study, adverse events will be assessed at Virtual Visit 6 and carbon monoxide levels from In-Person Lab Visit 3. Adverse events will typically be identified during the administration of the Health Changes Questionnaire. Other adverse events may be identified by spontaneous reports from the participant. Withdrawal symptoms are considered an adverse event if the symptom had a significant impact on the participant's daily life, caused a major disruption of functioning, or took any medication for it.

- **Health Changes Questionnaire:** If the participant answers "YES" to Questions 1, 2, or 3 the interviewer should assess for adverse events.
 1. Have you had any negative changes in your physical or mental health since your last virtual visit? If yes, briefly describe.

2. Since your last virtual visit, have you received any form of medical care? If yes, briefly describe.
3. Have you had any changes in medication since your last visit?

Physiological data that will be reviewed:

1. CO level: The 'Adverse Event Form' will be completed if the average of two (or three) consecutive measurements in the same visit is:
 - o CO is greater than 50 ppm if CO at Screening/Baseline Visit is < 20 ppm.
 - o CO is greater than 60 ppm if CO at Screening/Baseline Visit is 20 – 34 ppm.
 - o CO is greater than 70 ppm if CO at Screening/Baseline Visit is 35 – 49 ppm.

For the participant's protection, participants will be withdrawn immediately from the study if any of the following occur:

1. Cardiovascular disease (CVD) event: Typically includes MI (heart attack), PTCA (angioplasty/stenting), bypass surgery, stroke, peripheral vascular disease (arterial blockages in arms or legs leading to procedure or surgery). Less common CVD problems would be new cardiac arrhythmias (e.g., new atrial fibrillation) or new valvular disease (e.g., mitral or aortic regurgitation).
2. DVT/PE (deep vein thrombosis/pulmonary embolism, i.e., blood clots in the venous system).
3. Suicide Attempt: A participant will be withdrawn if they attempt suicide at any time during participation in the study
4. Psychiatric Hospitalization: A participant will be withdrawn if they are hospitalized for psychiatric reasons at any time during participation in the study.

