5. Pregnancy: If a participant indicates they are pregnant at Virtual Visit 6 or In-Person Lab Visit 3, they will be withdrawn from the study, and this event will remain open until delivery. At that time the license medical monitor will contact the participant to ask a few questions about the baby's health and will update the open 'Adverse Event Form'.

The following will be monitored and can lead to the participant being withdrawn by the PI:

1. Expired breath CO >80 ppm
2. Any hospitalization or debilitation in which participation in the study could be detrimental to the recovery process. This will be self-reported by the participant and will be reviewed by the site PI and medical monitor to determine whether continued participation in the study is appropriate.
3. If a participant is behaving in an inappropriate or threatening manner, admits to lying about eligibility criteria, including omitting previous medical diagnoses and medications, is participating in other smoking research studies that could affect the primary outcome measures, does not follow study instructions, etc., then the PI can withdraw them from the study at the PI's discretion.
4. If a participant fails to attend her/his Virtual Visit 1 within the 21-day allowable visit window, they will not be eligible to reschedule the visit or continue participation in the study.

References

http://www.ncbi.nlm.nih.gov/entrez/query.fcgi?cmd=Retrieve&db=PubMed&dopt=Citation&list_uids=10465828
2. Kozlowski, L. T. (2015). Prospects for a nicotine-reduction strategy in the cigarette endgame: Alternative tobacco harm reduction scenarios. *International Journal of Drug Policy*, 26(6), 543-547. doi:10.1016/j.drugpo.2015.02.001
3. Kozlowski, L. T. (2016). Cigarette prohibition and the need for more prior testing of the WHO TobReg's global nicotine-reduction strategy. *Tobacco Control*. doi:10.1136/tobaccocontrol-2016-052995
4. Kozlowski, L. T. (2017). Let actual markets help assess the worth of optional very-low-nicotine cigarettes before deciding on mandatory regulations. *Addiction*, 112(1), 3-5. doi:10.1111/add.13515
5. Shatenstein S. Eliminating nicotine in cigarettes. *Tob Control* 1999;8(1):106; author reply 07-9
http://www.ncbi.nlm.nih.gov/entrez/query.fcgi?cmd=Retrieve&db=PubMed&dopt=Citation&list_uids=10465827

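### No CO reading requires an Adverse Event Form for participants enrolled at a baseline of 50 to 80 ppm: a minor gap in safety recording

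*Combined protocol and SAP*

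**What the plan says.** All of this is in the combined protocol and SAP.

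- **Eligibility.** The inclusion list asks for "Breathe carbon monoxide (CO) level > 8 ppm or positive urine NicCheck" and sets no ceiling. The ceiling is in the exclusion list: "CO reading > 80 ppm". The qualifying CO is measured at In-Person Lab Visit 1.
- **Form rule.** Under Identifying Adverse Events (physiological data), the Adverse Event Form must be completed when "the average of two (or three) consecutive measurements in the same visit" exceeds a threshold set by the participant's baseline. There are three bands: above 50 ppm for baselines under 20, above 60 ppm for baselines of 20 to 34, and finally "CO is greater than 70 ppm if CO at Screening/Baseline Visit is 35" to 49 ppm. There is no higher band and no catch-all.
- **Withdrawal rule.** Later in the same section, an expired CO above 80 ppm is listed under the lead-in "The following will be monitored and can lead to the participant being withdrawn by the PI". That entry names no visit and no baseline, and does not mention the form.
- **Other routes.** Adverse events are usually found through the Health Changes Questionnaire, given to everyone at Virtual Visit 6. In addition, "Other adverse events may be identified by spontaneous reports from the participant".
- **When CO is taken.** CO is measured at all three lab visits. At In-Person Lab Visit 2, where "Participants will provide CO readings be at least 6-feet away from other people", the study products are also handed over: "Participants will be given the products they purchased during the ETM task". The adverse-event section names the CO from In-Person Lab Visit 3.

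**The concern.** The form rule is written as mandatory, and its threshold rises with baseline so that habitual heavy smokers are not flagged for their usual level. It then stops at 49 ppm, although eligibility runs to 80 ppm. Followed to the letter, it lapses for the participants who enter with the highest CO, and the documents give no reason for this.

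What is at stake is consistency of safety recording. Below a baseline of 50 ppm, a high reading has to be written up as an adverse event. From 50 ppm upward, whether it is written up depends on the judgement of whoever takes the reading. The other adverse-event routes rest on what the participant reports, so a high reading without symptoms need not surface through them.

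**Working it through.** The plan states no figure to reproduce here. The check applies the written rules to each eligible baseline, in whole ppm.

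**Inputs:** the CO ceiling of 80 ppm (exclusion criteria); the three bands and their thresholds, and the withdrawal cutoff of above 80 ppm (both in Identifying Adverse Events).

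**Step 1: coverage.**

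| Baseline CO (ppm) | Average that requires a form | CO above 80 ppm can lead to withdrawal |
|---|---|---|
| below 20 (8 or less enters by positive NicCheck) | above 50 | yes |
| 20 to 34 | above 60 | yes |
| 35 to 49 | above 70 | yes |
| 50 to 80 | none stated | yes |

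**Step 2: what the gap does.**

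- Baseline 49, average 75: 75 > 70, so a form is required.
- Baseline 50, average 100: no band applies, so none is required. The withdrawal rule applies, since 100 > 80.
- An average of 85 exceeds 50, 60 and 70, so it requires a form at every baseline up to 49 and at none from 50 to 80. It exceeds the withdrawal cutoff at all of them.

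**Step 3: the two forms of the fix are equivalent.** Suppose the form is required whenever the average exceeds 80 ppm. At baselines up to 49 this adds nothing, because an average above 80 already exceeds 50, 60 or 70. At baselines of 50 to 80 it is the missing band. The cutoffs then run 50, 60, 70, 80.

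**Step 4: the rise needed to trigger a form.** Smallest rise = smallest whole-ppm average above the threshold, minus baseline.

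- Existing bands, at the top of each, where the rise is smallest: 51 − 19 = 32, 61 − 34 = 27, 71 − 49 = 22 ppm.
- New band: 81 − 50 = 31, 81 − 60 = 21, 81 − 70 = 11, 81 − 80 = 1 ppm.

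The added band therefore continues the sequence of cutoffs but not the size of rise required. From baseline 60 upward the rise falls below the 22 ppm minimum of the existing bands.

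**Step 5: what stays uncovered.** With a cutoff of 80 ppm, an average of 80 or less at a baseline of 50 to 80 still needs no form.

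**The case against.** The strongest reply is that the readings that matter already receive attention. CO above 80 ppm is monitored in every participant and can lead to withdrawal, and a fourth band set at 80 ppm would catch only readings that this rule already covers. One could read it as the unwritten top tier after 50, 60 and 70. This reply stands in large part and is why the point is minor. It does not close the gap: the withdrawal entry is discretionary, concerns removal from the study and says nothing about the form. The pregnancy entry, in the list of immediate withdrawals, does refer to the form, so the protocol can name it in a withdrawal rule.

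Timing also limits the consequence. If CO is reviewed for adverse events only at In-Person Lab Visit 3, the seven days of field use are over, and a missing form cannot change exposure. At In-Person Lab Visit 2, where it could, the withdrawal rule applies.

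Three stronger readings are tempting, and the documents support none of them.

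- *High-CO participants go unmonitored, or a form is barred for them.* CO is taken at all three lab visits, the withdrawal rule covers every baseline, the questionnaire and spontaneous reports still operate, and nothing stops staff from opening a form.
- *More than a third of participants are affected.* The range 50 to 80 holds 31 of the 81 whole-ppm values from 0 to 80, or 38%. That counts possible values, not people. The documents give no distribution of baseline CO, and the values are not equally likely.
- *The trial's conclusions are at risk.* The primary outcome is cigarettes purchased in the marketplace task. The form rule does not enter its analysis or the power calculation.

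**Conclusion.** The point holds as a minor gap in safety recording. Eligibility reaches 80 ppm and the mandatory CO trigger for the form ends at a baseline of 49 ppm, so for anyone enrolled at 50 to 80 ppm no CO reading requires a form.

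How many participants this touches cannot be derived from the documents. With a target of 64 completers from up to 100 recruits, it is probably few, but that is a judgement. The conclusion assumes that baseline means the qualifying reading at In-Person Lab Visit 1, that CO is read in whole ppm, and that the list of bands is complete as printed. There is no mark of redaction at its end.

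**What to change.** In the list of events that can lead to withdrawal, add to the CO entry that an average above 80 ppm, over two or three readings at the same visit, also requires the Adverse Event Form. Equivalently, add a fourth band to the form rule: form required above 80 ppm when baseline is 50 to 80 ppm. Either way, state the averaging explicitly, because the withdrawal entry does not specify it, and have the medical monitor confirm the threshold.

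The cost is one protocol line and no new measurement. The drawback is an occasional form for a trivial rise near the ceiling: 1 ppm is enough at baseline 80, against at least 22 ppm in the existing bands. The medical monitor could avoid this by also requiring a minimum rise from baseline, at the price of leaving some readings above 80 ppm without a mandatory form. For illustration, borrowing the existing minimum of 22 ppm would put the trigger at 80 + 22 = 102 ppm for a baseline of 80. Any such condition should apply to the form only and leave the 80 ppm withdrawal rule as it is.
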